#### **6.2.4. Concomitant Medications, Vaccinations, and Blood Products**

The following concomitant medications, vaccinations, and blood products will be summarized:

- Antibiotics, including number of days of antibiotic use.
- Systemic steroids.
- Intrapinal steroids.
- Nonstudy vaccines.
- Blood products, including number of units and type (eg, whole blood, packed red blood cells [RBCs], platelets, and plasma). In addition, whole blood and packed RBCs will be identified as heterologous or autologous donations. Use of cell saver will be analyzed.

Statistical methodology is described in [Section 8.1.2.4](#).

### 6.3. Other Endpoints

#### 6.3.1. Demographic, Medical History, and Baseline Characteristics

Disposition variables will include enrolled, randomized, vaccinated, completed, and discontinued. Discontinuations will be split into reasons for discontinuation.

The demographic characteristics will include sex, race, racial designation (completed only if race = Asian), ethnicity, and age on the day of vaccination. Age on the day of vaccination will be derived in years ( $[\text{vaccination date} - \text{date of birth} + 1]/365.25$ ) and truncated to 0 decimal places. For subjects randomized but not vaccinated, the randomization date will be used instead of the vaccination date in the calculation of age.

Colonization status at baseline (Visit 1 or/and Visit 2 admission sample) will be compiled separately for each anatomical site (nose and throat), as well as “any anatomical site” (meaning both sites combined). The definition of colonization status when combining sites is described in [Section 8.1.4](#).

Body mass index (BMI), vital signs, colonization status at baseline, smoking status, alcohol consumption, and elapsed days from vaccination to index surgery will be summarized.

- BMI will be calculated as (weight [kg]/height [m] squared) and rounded to 1 decimal place.
- Vital signs include temperature (°C or °F), blood pressure (systolic and diastolic), pulse rate, and respiratory rate. All temperatures will be converted to °C.
- Alcohol consumption will be recorded as yes/no. If “yes,” then the number of units per week will be recorded.
- Elapsed days from vaccination to the index surgery will be the date of the index surgery minus the date of vaccination, plus 1.

Medical history data will be categorized according to the Medical Dictionary for Regulatory Activities (MedDRA) and summarized by vaccine group.

The Charlson Comorbidity Index (CCI) is a validated prognostic indicator for which factors, individually or in combination, may increase the risk of short-term mortality for subjects enrolled in longitudinal studies. On completion of the physical examination at Visit 1, the investigator will record the presence of each comorbid condition and age cohort as presented in [Table 5](#). The sum of the values for each comorbid condition is added to the subject’s value for age to obtain the CCI score. The 10-year mortality probability is calculated as  $0.983^{\text{EXP}[0.9 \times \text{CCI score}]}$  (Kastner et al).

**Table 5. Charlson Comorbidity Index**

Comorbid Condition	Score	Value for Age (on the Date of Assessment)
History of prior myocardial infarction (not ECG changes only)	1	Age <50 years: 0 points Age 50-59 years: 1 point Age 60-69 years: 2 points Age 70-79 years: 3 points Age 80-89 years: 4 points
Congestive heart failure	1	
Peripheral vascular disease	1	
Cerebrovascular disease	1	
Dementia	1	
Diabetes	1	
Mild liver disease	1	
Chronic pulmonary disease	1	
Gastric/duodenal ulcer	1	
Connective tissue disease	1	
Hemiplegia	2	
Moderate or severe renal disease	2	
Diabetes with end-organ damage	2	
Tumor	2	
Leukemia	2	
Lymphoma	2	
Moderate or severe liver disease	3	
Metastatic solid tumor	6	
AIDS	6	

Abbreviations: AIDS = acquired immunodeficiency syndrome; ECG = electrocardiogram.

The anesthesiologist will assess the subject's physical status before surgery using the American Society of Anesthesiologists (ASA) score; see [Table 16](#). Anesthesiologists use the ASA physical status classification system to assess the fitness of surgical patients before undergoing surgery. ASA scores correlate with patient morbidity and postoperative infection risk.

**Table 6. American Society of Anesthesiologists (ASA) Physical Status Classification**

Score	Description
1	Healthy patient
2	Mild systemic disease with no functional limitation
3	Severe systemic disease with definite functional limitation
4	Severe systemic disease that is a constant threat to life
5	Moribund patient unlikely to survive 24 hours with or without operation

Adapted from American Society of Anesthesiologists. ASA physical status classification system. Available: <http://www.asahq.org/Home/For-Members/Clinical-Information/ASA-Physical-Status-Classification-System>. 18 Jun 2014.

Statistical methodology for demography is described in [Section 8.1.3.1](#).

### 6.3.2. Index Surgery and Hospitalization

Surgical characteristics are listed below. Similar characteristics are collected for index surgery reoperation/revision. Variables are classified as categorical (meaning only discrete responses are possible) or numeric. Categorical variables are subdivided into 1 response per subject and multiple responses possible per subject.

One categorical response per subject:

- Any decolonization measures.
- Initial or revisional index surgery.
- *S aureus*/methicillin-resistant *S aureus* (MRSA) carriage evaluation performed.
- Preoperative skin preparation.
- Wound classification.
- Primary incision site.
- Primary skin closure type.
- Graft type.
- Implant material (type and composition)
- Intrawound application of an antibiotic.
- Prophylactic antibiotics administered within 1 hour before incision.
- Prophylactic antibiotics readministered during the index surgical procedure.
- Index surgery modified to be a staged procedure, performed on separate days.
- Evidence of malignancy during the index surgery.
- Evidence of infection during the index surgery.
- Temperature after surgery, using the categories defined in [Table 4](#).
- “Any fever,” defined as temperature  $\geq 38.0^{\circ}\text{C}$ .
- Type of glucose measure (capillary or serum).
- Been in an ICU.
- Location prior to hospital admission.

- Discharge disposition.

Multiple categorical responses possible per subject:

- Indication for surgery.
- Decolonization measure employed.
- Incision site hair removal method.
- Implanted devices.
- Vertebrae fused.
- Specialty of the surgeon, using the categories “orthopedic,” “neurosurgeon,” “orthopedic and general,” “neurosurgeon and general,” and “all others.”

Numeric responses from the subject:

- Intraoperative blood loss (mL) (Where blood loss is unknown, the default value is '0' – this will be handled as a missing value in the analysis)
- Number of vertebrae fused.
- Duration of surgery (in minutes), obtained as the time of the last suture minus the time of the first incision, plus 1.
- Duration of hospitalization (numeric: the date of discharge minus the date of admission, plus 1). Missing if the subject was not discharged.
- Number of days the subject was in an ICU (limited to subjects who were in such a unit) associated with the index surgery.
- Glucose values will be collected before the surgery and on the day after surgery. Each value will be identified as fasting (yes/no).

Statistical methodology for surgery and hospitalization is described in [Section 8.1.3.2](#).

### **6.3.3. Healthcare Utilization**

The healthcare utilization endpoints include:

- Location prior to hospital admission.
- Days in hospital.
- Ongoing in hospital (ie, not discharged).

- Discharge disposition:
  - Home self-care
  - Home healthcare
  - Rehabilitation facilities
  - Nursing home/skilled nursing care facility/nursing home
  - Death
  - Other
- Readmission related to complications of the index surgery.
- Proportion of readmissions to hospital.
- Proportion of readmissions to hospital related to complications of the index surgery.
- Proportion of subjects with additional surgery (the denominator will be the number readmitted for complications).
- Proportion in the ICU during readmission (denominator is the number of readmitted subjects).
- Number of days in the ICU, limited to subjects with hospital readmission related to complications for surgery.
- Proportion of subjects discharged from the hospital after readmission (denominator is the number of readmitted subjects).
- Total duration of hospitalization from the index surgery and any readmissions.
- Total days in an ICU from the index surgery and any readmissions.
- Number of rehabilitation/physical therapy visits as an outpatient.
- Inpatient days in rehabilitation facility or skilled nursing facility after discharge.
- Number of service visits (meaning skilled nursing home/skilled nursing facility or rehabilitation facility); discharges from the hospital to either of these will not count as a service visit.

The duration of each hospitalization episode will be the last day minus the first day, plus 1. Duration will be missing for episodes ending as “ongoing.”

Statistical methodology for healthcare utilization is described in [Section 8.1.3.3](#).

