9.4.2. Healthcare Utilization

Healthcare utilization will be determined for each vaccine group and will include days in hospital, days in an ICU, discharge disposition, inpatient days in skilled nursing or rehabilitation facilities after discharge, number of readmissions to hospital, number of reoperations, days of antibiotic use, and outpatient visits for rehabilitation/physical therapy. Descriptive statistics will be calculated for each vaccine group. Two-sided 95% CIs for the mean or median difference between vaccine groups will be obtained where applicable (ie, not for categorical responses such as postdischarge disposition). Comparisons of healthcare use will be performed between vaccine groups for the per-protocol, mITT, and safety populations.

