### **8.1.3.3. Healthcare Utilization**

Healthcare utilization variables whose units are days (eg, number of days in an ICU) will be summarized by sample size, mean, standard deviation, median, minimum, and maximum. Vaccine groups will be compared using the van Elteren test, with site as the stratification variable.

Categorical variables (eg, interventional procedures, discharge disposition) will be summarized by frequency counts and proportion of subjects in each category. If a subject has more than 1 hospital admission leading to more than 1 response, only the earliest hospital admission will be included in the analysis. Vaccine groups will be compared using the CMH method, with site as the stratification variable.

The number of service visits will be summarized by sample size, mean, standard deviation, median, minimum, and maximum. Vaccine groups will be compared using the van Elteren test.

The number of rehabilitation/physical therapy visits will be summarized by sample size, mean, standard deviation, median, minimum, and maximum. Vaccine groups will be compared using the van Elteren test.

Zeroes will not be imputed to subjects without the indicated response, eg, number of days in a skilled nursing facility.

All healthcare variables will be reanalyzed, but limited to subjects from the mITT efficacy population who have at least 1 PDI. Subjects with more than 1 PDI may be included in more than 1 analysis. There will be 6 additional analyses, 1 for each type of PDI (BSI and/or deep incisional or organ/space SSI, SSI, or ISA disease) by 2 windows (1-90 and 1-180 days). Vaccine groups will be compared in numeric variables using the Mann-Whitney test and compared in categorical variables using the Fisher exact test. The statistical tests will not incorporate site because the number of PDIs per site will be small or zero.

Statistical analyses for healthcare utilization are summarized in [Section 8.2.3.3](#).

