**Table 24. Summary of Healthcare Utilization Analyses**

Endpoint	Population	Statistical Method	Stratification	Missing Data	Interpretation/Comments
Categorical healthcare utilization: 
 
• location prior to hospital admission
 
• ongoing hospitalization, yes/no
 
• discharge disposition
 
• proportion of readmissions to hospital
 
• proportion of readmissions related to complications of index surgery
 
• additional surgery
 
• proportion in an ICU in readmission
 
• proportion discharge after readmission
 
	mITT	CMH	Site	N/A	Impact of vaccination on subsequent healthcare use
Numeric healthcare utilization: 
 
• duration of hospitalization
 
• number of readmissions related to complications of index surgery
 
• number of days in the ICU
 
• total hospitalization from index surgery and any readmissions
 
• total days in ICU from index surgery and any readmissions
 
• number of service visits
 
• number of inpatient days in rehabilitation or nursing facility
 
	Any subject with PDI	Mann-Whitney	N/A	N/A	Impact of vaccination on subsequent healthcare use, limited to subjects with PDIs  Performed for PDIs in 1-90 and in 1-180 days

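### Hospital episodes that have not ended are given no duration, so known inpatient days drop out of the exploratory length-of-stay comparisons, and total days are left undefined when one episode is open

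*SAP*

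**What the plan says.** Two SAP sections carry the rule. For the index admission (6.3.2), duration runs from admission to discharge: "Missing if the subject was not discharged". For healthcare utilization (6.3.3), "The duration of each hospitalization episode will be the last day minus the first day, plus 1", followed by "Duration will be missing for episodes ending as" ongoing. The same section equates ongoing with not discharged. It also defines an endpoint that totals hospital days over the index stay and all readmissions.

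For variables measured in days, SAP 8.1.3.3 says: "Vaccine groups will be compared using the van Elteren test, with site as the stratification variable". In the re-analysis limited to mITT subjects with a PDI (three endpoint types by two time windows, six analyses), "Vaccine groups will be compared in numeric variables using the Mann-Whitney test and compared in categorical variables using the Fisher exact test". SAP 8.1.3.2 also compares duration of hospitalization by van Elteren. Protocol 9.4.2 promises an estimate as well: "Two-sided 95% CIs for the mean or median difference between vaccine groups will be obtained where applicable".

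Ongoing status is analysed in its own right. SAP Table 24 lists "ongoing hospitalization, yes/no" among the categorical variables, compared by CMH in the mITT population and by Fisher exact test among subjects with a PDI.

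**The concern.** A stay that is still open is right-censored: its true length is at least the days observed so far. Setting it to missing discards that information, and the reason for the loss is the outcome itself, since longer stays are more likely to be open when observation stops. An index stay open at the end of follow-up belongs at the top of the ranking, and the rule takes it out. If one arm has more open stays, the duration comparison is tilted in that arm's favour.

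Protocol 1.2.1 says that inpatients with *S aureus* infection stay about three times as long as others. Prolonged stays are therefore where an effect of vaccination on hospital use would be expected to show.

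There is also a gap in definition. If a subject has a completed index stay of a days and an open readmission with b days so far, the SAP text allows a total of missing or a total of a. Neither uses the known total of at least a + b, and two programmers could produce different tables.

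**Working it through.** **1. Is the loss repaired elsewhere?** No. The sensitivity analyses in SAP Section 7 deal with missing microbiology for the primary and secondary efficacy endpoints. The no-imputation statement there lists immunogenicity, safety, demographic and colonization variables, not healthcare utilization. No censoring, worst-rank or other rule is given for missing durations. The yes/no comparison counts open stays but carries no days.

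**2. Which stays are affected?** Those with no recorded discharge at study completion, at withdrawal, or at a data cut-off. Death is listed as a discharge disposition (Protocol Appendix 4, SAP 6.3.3), so a stay that ends in death appears to keep its duration.

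**3. A figure to reproduce?** The documents state no sample size, power or expected value for length of stay. The case numbers from Protocol 9.2 can be used to set the scale:
- Subjects per arm: 6000 × 0.9 / 2 = 2700.
- Expected cases: 2700 × 0.014 × (1 + 0.30) = 49.1, against the 48 stated.
- Split of 48 cases at VE 70%: 48 × 0.30/1.30 = 11.1, so about 11 SA4Ag and 37 placebo.

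**4. Illustration, full set.** Assumed inputs, not from the documents except the factor of 3: lognormal stays with median 5 days and log-SD 0.5, three times as long if infected, one stay per subject, and ongoing stays set to 180 days. There were 2700 subjects per arm, VE 70%, 400 simulated trials and an unstratified Mann-Whitney test. Differences are SA4Ag minus placebo.

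| Infected subjects still in hospital | Stays dropped (SA4Ag / placebo) | Mean difference, kept | Mean difference, dropped | Rejection, kept | Rejection, dropped |
|---|---|---|---|---|---|
| 5% | 0.6 / 2.0 | −0.20 d | −0.11 d | 8.0% | 7.8% |
| 10% | 1.1 / 3.7 | −0.26 d | −0.10 d | 8.3% | 7.0% |
| 20% | 2.1 / 7.3 | −0.42 d | −0.08 d | 8.8% | 7.0% |

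The Monte Carlo standard error of a rejection rate near 8% is √(0.08 × 0.92 / 400) = 1.4 points, so the rank test hardly moves. The mean difference shifts by a fraction of a day, driven by the assumed 180-day value.

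**5. Illustration, PDI-limited set.** Assumed: 11 vs 37 cases, median 15 days (5 × 3), log-SD 0.5, no arm difference among stays that ended, 4000 simulations.

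| Ongoing, placebo / SA4Ag | Rejection, ongoing ranked highest | Rejection, ongoing dropped |
|---|---|---|
| 5% / 0% | 4.6% | 4.5% |
| 10% / 0% | 6.6% | 4.5% |
| 20% / 0% | 14.6% | 5.0% |
| 5% / 5% | 4.6% | 5.1% |
| 10% / 10% | 4.5% | 4.3% |
| 20% / 20% | 4.9% | 4.2% |

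Dropping the open stays removes a signal only when they are unequally distributed between arms. With equal fractions nothing material changes.

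**The case against.** The strongest reply is that the stays are not lost. Ongoing status is its own endpoint and is compared between arms, so an excess of unresolved stays would be displayed and tested; duration is then simply a variable defined for completed episodes. This stands in part: an imbalance would be seen. But the day counts, and the mean or median difference that the protocol promises, would still leave out days that are known.

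Three further points stand.
- The comparison is an exploratory objective, and no decision rule depends on it.
- The snapshot problem is limited. Protocol 9.6 places analyses of this kind after database lock. SAP Section 3 does allow unblinded tables from a snapshot, but it also calls for a supplementary report once all subjects have completed.
- An unequal share of open stays is not assured. SAP 8.1.3.5 records that the study met its futility criteria at the interim analysis.

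A reader might infer that the rule removes the longest, mostly infection-related stays and with them a large part of any difference between arms. The documents do not support that. They give neither the share of stays left open nor the share of those due to infection; the threefold figure is background on *S aureus* inpatients in general. A readmission shortly before cut-off, or a stay cut short by withdrawal, need not be long. Large open fractions are also hard to reach with follow-up to Day 180. Assuming lognormal stays with a median of 20 days and log-SD 0.79, the share beyond 180 days is 1 − Φ(ln(180/20)/0.79) = 1 − Φ(2.78) = 0.27%, far from the 8% to 16% that a large distortion would need.

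**Conclusion.** The point holds as a minor one. Two SAP sections delete known inpatient days because a stay has not ended, nothing in the plan repairs this for the duration comparisons, and total hospital days are undefined when an episode is open.

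The effect is likely to be very small in the full mITT set at study end. It could matter in the PDI-limited analyses or in tables run on a snapshot, and only if ongoing stays differ between arms. No percentage loss of effect or power can be attached to it, because the documents give no ongoing fraction; the tables above show how the result depends on assumed fractions and are not estimates for this trial. The primary efficacy conclusion is not affected.

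**What to change.** In SAP 6.3.2 and 6.3.3:

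- Define days in hospital and total duration as days observed within follow-up. Count an ongoing episode to the last date on which the subject was known to be in hospital (study completion, withdrawal or data cut-off). Total duration is then the sum over completed and ongoing episodes.
- Add a sensitivity analysis for the van Elteren and Mann-Whitney tests that gives ongoing episodes the highest rank. It is needed because counting to the last known date treats a censored stay as complete in a per-episode rank test: an admission shortly before cut-off would rank among the shortest.
- Show the already planned ongoing counts per arm beside each duration result.

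The cost is SAP wording and one extra exploratory analysis. Protocol 6.3.1.2.1 and 6.4.3 require daily assessment during the index stay and later hospitalizations, so a last known inpatient date should be available. The remaining limitation is that the counted days are still a lower bound for open stays, and the tables should say so.

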#### **6.3.4. Colonization with *Staphylococcus aureus***

If 2 or more samples associated with postsurgery are obtained, only the colonization results from the latest visit will be eligible for analysis.

Four colonization endpoints, based on colonization results from scheduled visits, are specified:

1. The number and proportion of subjects in each vaccine group determined to be colonized with *S aureus* on each scheduled visit where swab samples are collected. Colonization at each visit will be compiled separately for each anatomical site, and for any anatomical site. A subject will be considered positive for “any anatomical site” if either site, or both, is positive.
2. Subject carriage status will be characterized across visits as persistent, indeterminate, intermittent, or noncarrier. Characterizations will be performed by anatomical site and any anatomical site. Characterizations will be based on number of visits where colonization results were obtained, limited to Visits 1, 2 (both the day of surgery and the day of discharge), 4 (Day 42), 5 (Day 90), and 6 (Day 180). Rules for determining carriage status are described next and are also illustrated in [Table 7](#).
  - Persistent: positive at 4 of 5, 5 of 5, 5 of 6, or 6 of 6 visits.
  - Indeterminate: exactly 3 or 4 visits, regardless of combination of positive/negative results.
  - Intermittent: positive at 1 or 2 visits if 2 visits are available, positive at 1 to 3 visits if 5 visits are available, positive at 1 to 4 visits if 6 visits are available.
  - Noncarrier: no positive results at any visit, minimum of 5 visits.

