**Table 7. Rules for Determining Carriage Status**

No. Positive Results							
No. Visits Available	0	1	2	3	4	5	6
1	Missing	Missing	N/A	N/A	N/A	N/A	N/A
2	Missing	Intermittent	Intermittent	N/A	N/A	N/A	N/A
3	Indeterminate	Indeterminate	Indeterminate	Indeterminate	N/A	N/A	N/A
4	Indeterminate	Indeterminate	Indeterminate	Indeterminate	Indeterminate	N/A	N/A
5	Noncarrier	Intermittent	Intermittent	Intermittent	Persistent	Persistent	N/A
6	Noncarrier	Intermittent	Intermittent	Intermittent	Intermittent	Persistent	Persistent

Abbreviation: N/A = not applicable.

3. Acquisition is defined as a positive swab at any postsurgery visit, given that the results for the vaccination and presurgery visits were both negative. The proportions of acquisitions will be compiled for each subsequent postsurgery visit and “any postsurgery visit.” The denominator at each visit will be the number of subjects with at least 1 nonmissing swab result. Acquisition will be compiled for nose, throat, and “any anatomical site.”
4. Clearance is defined as 2 consecutive postbaseline negative swabs, given that all preceding swabs were positive. The proportions of clearances will be compiled for each postbaseline visit. The denominator at each visit will be the number of subjects with at least 1 nonmissing swab result. The analyses will be performed for nose, throat, and “any anatomical site.”

Colonization, carriage status, acquisition, and clearance will be compiled for “any *S aureus*,” MRSA, and methicillin-sensitive *S aureus* (MSSA).

Capsule type will be identified for each *S aureus* isolate as either CP5 or CP8. A small subset of isolates will be neither capsule type, so these isolates will be considered missing for capsule type. Carriage status, acquisition, and clearance will be obtained for each capsule type. These endpoints will be identified as capsule-type persistence, capsule-type intermittent, capsule-type noncarrier, capsule-type acquisition, and capsule-type clearance. Analyses with these endpoints may be performed.

Other endpoints based on clonal complex (CC) and sequence type (ST) may be explored. *S aureus* protein A (*Spa*) typing and capsule typing may be examined only for PDIs with microbiologically confirmed *S aureus* infection.

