#### **8.1.3.4. Colonization with *Staphylococcus aureus***

Colonization values obtained up to 7 days before vaccination until the day of admission for surgery will be considered eligible baseline values.

Colonization at each visit, acquisition, and clearance are binary endpoints, so they will be summarized with proportions. Vaccine groups will be compared using the CMH test. Site will be the stratification variable.

Carriage status will form a  $3 \times 2$  table with 3 categories—“persistent,” “intermittent,” and “noncarrier”—and 2 vaccine groups. “Indeterminate” will be considered a missing value. Vaccine groups will be compared using the CMH test. Site will be the stratification variable.

Subgroup analyses will be performed by executing logistic regressions with the dependent variable of the proportion of subjects colonized. The model terms will be vaccine group, subgroup, and vaccine group–subgroup interaction. The colonization results for subgroups with significant interactions, defined as  $p < 0.10$ , will be examined more closely.

One subgroup will be examined at a time. Anatomical sites will be examined separately. Only colonization at scheduled visits will be included. Only *S aureus* colonization will be analyzed because the purpose is to see if vaccine group has different effects within subgroup levels.

Vaccine groups will be compared using the Fisher exact test, 2-sided, for the proportion positive for *S aureus* from unscheduled visits. Stratification by clinical site is not proposed because the unscheduled visits will presumably be associated with possible BSI/SSI/ISA.

The number of these assessments per site should be low. Analyses will be performed by anatomical site and for anatomical sites combined.

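### The carriage rule lets a subject with two visits into the carriage comparison only if a visit was positive, and then always as Intermittent

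*SAP*

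**What the plan says.** SAP Section 6.3.4, second colonization endpoint, assigns each subject a carriage status across as many as six swab occasions: Visit 1, day of surgery, discharge, Day 42, Day 90 and Day 180. The unit is the visit with a result: "Characterizations will be based on number of visits where colonization results were obtained".

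- Intermittent includes "positive at 1 or 2 visits if 2 visits are available".
- The rule for three or four visits is "Indeterminate: exactly 3 or 4 visits, regardless of combination of positive/negative results".
- The rule for no positives is "Noncarrier: no positive results at any visit, minimum of 5 visits".

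Table 7 agrees with the text. For 0, 1 and 2 positives, its two-visit row reads "Missing Intermittent Intermittent".

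SAP Section 8.1.3.4 then compares vaccine groups by a CMH test stratified by site, in a "table with 3 categories" (Persistent, Intermittent, Noncarrier). It says that Indeterminate "will be considered a missing value". The SAP gives no reason for classifying two-visit subjects when those with three or four visits are not classified.

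**The concern.** Whether a subject is analysed should depend on how much was observed, not on what was observed. Here a two-visit subject with two negatives is dropped, while one with a positive is kept. Those kept can only be Intermittent, so they raise that category and never add to Noncarrier.

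The labels also conflict. Three of three or four of four positive visits are called too few to classify. Two of two positive, with less information and no negative seen, is called Intermittent.

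At stake is the carriage-status table, compiled for nose, throat and any site, and for any *S aureus*, MRSA and MSSA. The endpoint is exploratory.

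**Working it through.** The plan states no figure on this point, so there is none to reproduce. The check has two steps.

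**Step 1. Who enters the three-category table.** The text rules of SAP Section 6.3.4 were compared with all 27 cells of Table 7 (1 to 6 visits, with 0 positives up to the number of visits). They agree in every cell, taking cells that no text rule covers as Missing. Applying SAP Section 8.1.3.4 gives:

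| Visits with results | Status possible | Enters the table? |
|---|---|---|
| 1 | Missing | Never |
| 2, none positive | Missing | No |
| 2, one or two positive | Intermittent | Yes |
| 3 or 4 | Indeterminate | Never |
| 5 or 6 | Noncarrier, Intermittent or Persistent | Always |

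Only at two visits does the result decide entry.

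**Step 2. Illustration of size.** The documents give neither the number of two-visit subjects nor a positivity rate for this trial. Assumptions: per-visit positivity p from 20% to 50% (the Protocol introduction cites this range for colonization in humans generally, not for this trial); two-visit subjects a fraction f of 2% to 10%; all others with six visits.

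Share of two-visit subjects who enter:

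- Independent visits: 1 − (1 − p)². At p = 0.20 this is 1 − 0.64 = 36%. At p = 0.50 it is 1 − 0.25 = 75%.
- Results identical within subject: p itself, so 20% to 50%.
- Overall range: 20% to 75%.

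Effect on the pooled Intermittent share, against leaving out all two-visit subjects:

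- Independent visits. Among six-visit subjects the Intermittent share is 1 − (1 − p)⁶ − P(5 or 6 positive), which is 73.6% at p = 0.20 and 87.5% at p = 0.50. With f = 0.10 and p = 0.20, the share as written is (0.90 × 0.736 + 0.10 × 0.36) / (0.90 + 0.10 × 0.36) = 74.6%, a rise of 1.0 point. With f = 0.02 it is 73.8%, a rise of 0.2 points. At p = 0.50 the rises are again 0.2 points (to 87.7%) and 1.0 point (to 88.5%).
- Fully correlated visits. Six-visit subjects are then all Persistent or Noncarrier, so the Intermittent share starts at 0. As written it is fp / (1 − f + fp). With f = 0.02 and p = 0.20 this is 0.004 / 0.984 = 0.4%. With f = 0.10 and p = 0.50 it is 0.05 / 0.95 = 5.3%, and Noncarrier falls from 50.0% to 0.45 / 0.95 = 47.4%, a drop of 2.6 points.

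These are shifts in a pooled share. They are not estimates of a difference between arms.

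**The case against.** The best defence of the rule is that a positive swab proves carriage at that time, whereas two negatives are weak evidence of non-carriage. That would justify some asymmetry, but it does not explain this rule. The same reasoning would classify subjects with a positive among three or four visits, and the SAP declines to do so.

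The objections about consequence stand:

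- The two-visit row should be small. Operated subjects have swabs scheduled at Visit 1, before surgery and at discharge, which already makes three. SAP Section 5.5 excludes subjects without index surgery from colonization analyses. Reaching exactly two generally takes a missed swab or an infection before the discharge swab.
- Colonization is an exploratory objective (Protocol Section 2.4). The protocol's own endpoint, the number colonized on each swab occasion, does not use this rule.
- SAP Section 8.1.3.5 records that the trial met its futility criteria and ceased enrollment.

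A reader might infer that early infections push subjects into Intermittent and so bias the comparison of arms, because SAP Section 6.3.4 drops swabs taken after a culture-confirmed endpoint. The documents do not support that. A case with onset after discharge and before Day 42, with complete earlier swabs, keeps three visits and is Indeterminate whatever the results. A case falls in the two-visit row only if onset precedes the discharge swab or an earlier swab was missed. Cases are also few: the target is 48 per-protocol cases in about 6000 subjects, or 48/6000 = 0.8%. The rule is the same in both arms of a randomized, double-blind trial, and nothing in the documents shows that the number of two-visit subjects differs by arm.

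**Conclusion.** The rule is wrong as written, but the matter is minor. Two visits is the only count at which entry into the carriage table depends on the result, and all who enter are Intermittent, including those with two of two positive. Adding only Intermittent subjects necessarily raises that share. The conclusion about entry follows from the text and Table 7 alone and needs no assumption.

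The size is unknown. Under the stated assumptions, 20% to 75% of two-visit subjects would enter. The Intermittent share would rise by 0.2 to 1.0 points if visits are independent and by 0.4 to 5.3 points if results are fully correlated. The upper end needs both 10% two-visit subjects and 50% positivity.

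If the vaccine has no effect on carriage, the rule would bias the arm comparison only if two-visit subjects were more frequent in one arm. That is a possibility, not a finding. Primary efficacy is unaffected.

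**What to change.** In SAP Section 6.3.4, delete "positive at 1 or 2 visits if 2 visits are available" from the Intermittent bullet. In Table 7, set all three applicable cells of the two-visit row to Missing, as for one visit. Visit count alone then decides inclusion: none of the subjects with one to four visits is analysed, and all of those with five or six are. The one-visit row and the rule for three or four visits need no change.

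The cost is one clause and one table row, with no new data and no protocol change. A few subjects with two visits and at least one positive leave the carriage table. Their swabs still count in the visit-by-visit colonization proportions.
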